### ***6.11 Participant Withdrawal or Termination***

#### **6.11.1 Reasons for Withdrawal or Termination**

Participants are free to withdraw from participation in the study at any time upon request. If the nature of treatment makes immediate withdrawal unsafe, withdrawal may be tapered.

An investigator may terminate participation in the study if any situation occurs such that continued participation in the study would not be in the best interest of the participant or the integrity of the study.

Discontinuation of a study agent, regardless of the reason, e.g., patient or physician request, or adverse event, does not constitute study withdrawal. Patient data will still be collected as planned and analyzed as intention to treat unless the participant withdraws consent for continued follow-up.

#### **6.11.2 Premature Termination or Suspension**

The platform, or any arm of the study, may be temporarily suspended or prematurely terminated if there is sufficient reasonable cause. Circumstances outside of interim analyses that may warrant termination or suspension include, but are not limited to:

- Determination of unexpected, significant, or unacceptable risk to participants in a strategy, such as excess mortality or serious adverse treatment effects
- Insufficient compliance to the protocol requirements
- Insufficient accrual in a study arm

If the platform stops for safety, noncompliance, or data quality, it may resume once such concerns about safety, protocol compliance, or data quality are addressed and satisfy the requirements of appropriate oversight bodies including but not limited to the sIRB, the DSMB, and the FDA.

Decisions to stop a study arm or the platform based on the accruing data are not considered premature termination or suspension. They will be guided by the decision thresholds described in the statistical analysis plan and augmented by details in relevant Appendices. Such decisions will generally be weighed by the DSMB. Reasons for stopping based upon the data will include safety (DSMB review of AEs) or demonstration of inferiority.

## 7 Study Procedures and Schedule

### 7.1 Study interventions

Study agents are described in the agent-specific appendices.

A summary of the trial's schedule of events is listed in Section [7.7](#) and included in

Event	Baseline & Randomization Day 0	Day 1 – Day 28	Discharge	Day 60	Day 90
Visit Windows		Day 7 and 14 + 1 Day Day 21 + 2 Days Day 28 + 5 Days		+ 10 Days	+ 14 Days
Confirm eligibility	X				
Obtain informed consent	X				
Screen by reviewing medical history and EMR	X				
Pregnancy test	X				
Randomization	X				
Concomitant medications	X	X 			
Record results of SOC laboratory assessments	X 	X			
Study-specific blood draws 
 
CBC with diff and LFTs in fostamatinib arm
 
	X 	X			
Study-specific biological specimen collection 
 
EDTA plasma
 
Serum
 
	X 	X			
Respiratory failure free days, oxygen free days and hospital free days	X 	X	X		
WHO Ordinal Scale	X	X		X	
Mortality	X	X	X	X	X
Sequential Organ Failure Assessment score	X				
Initiate treatment	X				
Continue study medication treatment		X			
Adverse event monitoring	X	X 		X	

Record discharge disposition			X		
------------------------------	--	--	---	--	--

**Table 1** (Following section 7.7).

Timing of study procedures is based on the day and time of randomization, which sets Day 0 and Time 0. The primary outcome will be assessed on Study Day 28 or at the time of death.

Study medications will be administered by clinical or research personnel while the patient is hospitalized. The first dose of study medication will be administered within 6 hours of randomization. In the hospital, medication delivery after the first dose will correspond to the timing of other scheduled medication delivery for the hospital/unit when possible. If the patient is discharged, the study medication will be stopped unless the oral study medication is planned to be continued in the outpatient setting.

, On each day the participant is hospitalized and scheduled to receive study drug, study personnel will review patient records to confirm administration of study drug and document the number and reason for any missed doses. Research personnel will also assess patients daily during hospitalization for up to 28 days post-randomization. If the participant is discharged before the full 28-day period, data will be collected according to a set schedule (Day 1, 3, 7, 14, 21, and 28 post-randomization) beginning at the next corresponding day post-discharge. This includes data regarding oral study medication administration in those subjects who are randomized to arms with oral study medication. These assessments may be completed by phone or electronically (email, text, or survey link) if the patient has been discharged from the hospital. Patients in the fostamatinib arm could require an in-person visit depending on their clinical profile at the time of discharge. This is further defined in [Appendix D: Arm 3: Fostamatinib](#). At day 60 we will collect AEs, the WHO 8-point ordinal scale and assess vital status. A final contact will be made at day 90 to assess vital status.

### **7.2 Expedited Critical and Major Event Reporting**

All efficacy and safety outcome events will be assessed and documented in the patients' study records as outlined in section [13](#). Events meeting the DSMB-specified *expedited reporting* criteria must be reported immediately to the coordinating center and no later than 24 hours from knowledge of occurrence. Standing SOPs applicable to all sub studies will guide the reporting of adverse events to ensure they are assessed quickly and are submitted to the DSMB, IRB(s), sponsor and other groups as needed (e.g., FDA). All participating sites will also be expected to comply with any local requirements for reporting.

### **7.3 Data and Safety Monitoring Plan**

*[The data and safety monitoring plan (DSMP) is described briefly in Appendix B: Data and Safety Monitoring Plan and in detail in a separate DSMP document.]*

### **7.4 Biological specimens**

Participants in this Master Protocol are expected to contribute biological specimens for discovery. The biological specimens to be collected, including collection times, processing requirements, and storage and shipping, are described in Appendix C: Minimum Biological Specimen collection, and any additions to this minimum specimen collection will be described in relevant appendices.

### **7.5 Shared placebo group dose, duration, and route of administration**

Each active agent will have a matching placebo. Placebo formulations are described in the appendices for each agent.

### **7.6 Co-Interventions and Co-enrollment**

This trial will control the use of study medications (active and control) during the treatment window. Study arm specific medication contraindications are explained in detail in the study arm specific Appendices. All other treatment decisions will be made by treating clinicians without influence from the protocol. The decision to administer antiviral medications, including remdesivir or convalescent plasma, or immunomodulating medications, including corticosteroids, will be made by treating clinicians and will be recorded in the case report form. We expect usual care to evolve as the study progresses, and this will be defined by the most recent available evidence and local drug supply.

Sponsor and/or protocol leadership may, based upon convincing new evidence, act in the interest of participant protection, and in avoidance of confounding, to exclude/dis-allow use of any specific concomitant therapy found to be reasonably contraindicated for a well-defined portion of the study population. Such a determination may be made, communicated, and implemented by a Protocol Clarification Memo until it is reasonable to amend the protocol for other reasons.

Participants will be asked at screening to agree to refrain from participation in other clinical trials until at least the assessment at Day 90 except for trials comparing different approaches for implementing SOC interventions or those approved by trial leadership.

Co-enrollment in other trials will only be allowed in the US where a co-enrolling trial has been approved by trial leadership. We will consider several principles when considering co-enrollment in the Master Protocol.

- 1) This will only apply to clinical trials where there is open label enrollment to facilitate interim and final analyses of data for this trial, including treatment interactions, and the attribution of causality of serious adverse events and unanticipated problems.
- 2) Co-enrollment will not be permitted with trials involving medications with contraindications to co-administration with any study drug for which the participant is eligible. This review and consideration will be similar to consideration of concomitant medications. This assessment will occur prior to randomization in the ACTIV 4 Host Tissue platform. This ensures there are no specific drug-drug interactions in the event the patient is receiving active therapy in the assigned arm.
- 3) Trials involving medications impacting the RAAS pathway will not be considered.
- 4) Study procedures for the co-enrolling trial will be considered secondary to the procedures for the RAAS MP. We will aim to collect the primary and key secondary outcomes for the co-enrolling trial but consider the overall participant burden when fulfilling trial procedures for the co-enrolling trial such as additional blood draws and participant assessments.
- 5) Co-enrollment prior to randomization will be documented. The impact of co-enrollment on the effects of active agents versus placebo on the primary outcome (i.e., heterogeneity of treatment effect) will be examined as a supplementary analysis.

We aim to co-enroll with the ACTIV-4a trial only, an open-label randomized trial now studying the impact of P2Y12 inhibitors, SGLT2 inhibitors and crizanlizumab on top of usual care. Patients will be randomized in ACTIV-4a to one of these medications at a time in an open label fashion. There are no drug-drug interactions with agents in our platform. Patients co-enrolled in ACTIV-4 Host Tissue and the crizanlizumab domain of ACTIV-4a require 36 hours between administration of fostamatinib and the first crizanlizumab co-administration. Patients who receive both an SGLT2 inhibitor and fostamatinib need to be monitored for volume depletion. SGLT2 inhibitors can cause an osmotic diuresis and patients on fostamatinib may develop diarrhea. Based on the anticipated overlap in sites, similarity in inclusion and exclusion criteria, and willingness of patients to co-enroll in other ACTIV studies, we expect less than 5% of patients will be co-enrolled in ACTIV-4a.

## **7.7 On study monitoring**

All patients will be hospitalized at the time they are enrolled in the study and will therefore receive monitoring as a part of routine clinical care, including monitoring by their physicians, nurses, respiratory therapists, and ancillary staff. Clinical and laboratory data obtained as part of routine clinical monitoring will be collected. Those labs required to evaluate secondary and safety outcomes that are not collected as part of usual care will be obtained for the purpose of the study protocol as outlined in section [7.7.6](#).

### **7.7.1 Laboratory evaluations**

Routine clinical monitoring will follow laboratory results when measured as part of usual care which may include daily complete blood count (CBC), renal function (creatinine/eGFR), electrolytes, D-dimer, CRP, and measures of coagulation (PT/PTT/INR). In the fostamatinib trial a daily CBC and liver function tests will also be performed while in the hospital on study drug.

### **7.7.2 Clinical evaluations**

Between randomization and hospital discharge or end of study drug, study personnel will review the electronic health record daily for potential medication interactions with the host tissue agents being studied (see Appendix D). If a medication considered to be contraindicated with the host tissue agent is discovered, treating clinicians will be contacted to discuss if stopping study drug is appropriate or if the medication in question can be stopped or substituted. Those medications in the fostamatinib arm with absolute contraindications (Appendix D) will be held or study drug stopped. When there are relative contraindications treating clinicians will determine whether an alternative medication would be appropriate or whether the risk-benefit ratio favors continuing the medication with the known potential interaction.

### **7.7.3 Criteria for stopping drug**

Criteria for holding/stopping each trial drug are contained in the trial specific appendices (Appendix D).

To delineate reasons for study drug discontinuation, if study drug is discontinued the study team will be prompted to indicate why it was discontinued. There will be 3 options to choose from:

1. Logistical - i.e. loss of IV access, CT scan, transport, etc. – no AE reporting/recording required
2. Clinical events that did not represent an AE – i.e., Fostamatinib stopped due to starting contraindicated medication – no AE reporting/recording
3. Due to a possible AE or PSESE –study team directed to go to PSESE or AE reporting page in electronic data capture form.

### **7.7.4 Plan for drug shortages**

In the event of a shortage of study drug at a participating trial site, the trial arm will be suspended at that site, but the platform trial will continue.

### **7.7.5 Baseline variable collection**

Baseline is defined as the patient's status at randomization. Physiological measurements and laboratory results obtained in the 24 hours prior to randomization may contribute to baseline data. The baseline study-specific blood draws may be completed at any time between consent and the first dose of study medication. The following information will be obtained to reflect the patient's baseline status:

1. Confirmation of informed consent for trial participation
2. Confirmation of inclusion/exclusion eligibility criteria for trial participation

3. Confirmation of the participant not being pregnant including a study-dedicated pregnancy test for women of childbearing potential (WOCBP).
  - a. WOCBP are defined as any female who has experienced menarche, has not undergone surgical sterilization (hysterectomy, bilateral salpingectomy, or bilateral oophorectomy), and has not experienced menopause
  - b. Postmenopausal women, defined as someone who has gone through menopause, do not have to take a pregnancy test.
4. Admission data: date and time of presentation, origin (home, skilled nursing facility, rehabilitation/long-term-acute care hospital, nursing home, outside hospital, outside ICU), location at enrollment (ED, hospital ward, ICU)
5. Sociodemographics (such as age, sex, race, ethnicity, height, weight, poverty index)
6. Study-specific blood draws (AngII, Ang(1-7), ACE and ACE2, NTproBNP and Troponin) as indicated for each investigational agent in the Ancillary Biomarker Appendix (Appendix C: Minimum Biological Specimen collection).
7. Comorbidities such as: AIDS, Leukemia, Malignant Lymphoma, Hemiplegia, Cerebrovascular Disease, Prior Myocardial Infarction, Congestive Heart Failure, Peripheral Vascular Disease, Dementia, COPD, Connective Tissue Disease, Peptic Ulcer Disease, History of Hypertension, HIV positive (without AIDS), Alcoholism, Coronary Artery Disease, Solid Tumor, Liver Disease, Diabetes Mellitus, Chronic Kidney Disease
8. Acute signs and symptoms such as: altered mental status, acute hypoxemic respiratory failure, liver function tests, renal function, coagulation studies, chest imaging results
9. Sequential Organ Failure Assessment (SOFA)
10. Chronic use of medications, such as: corticosteroids, ACE inhibitors, angiotensin receptor blockers, non-steroids anti-inflammatory drugs, others
11. Receipt of antiviral medications between hospital presentation and randomization: chloroquine, hydroxychloroquine, remdesivir, lopinavir/ritonavir, others
12. Receipt of immunomodulators between hospital presentation and randomization: corticosteroids, tocilizumab, sarilumab, interferon  $\beta$ , others
13. Receipt of anticoagulation and anti-platelet agents between hospital presentation and randomization
14. COVID-19 vaccination status
15. Receipt of COVID-19 convalescent plasma between hospital presentation and randomization
16. Receipt of anti-SARS-CoV-2 monoclonal antibodies between hospitalization and randomization
17. Receipt of invasive mechanical ventilation, non-invasive ventilation, high-flow nasal cannula, vasopressors, and oxygen therapy at randomization
18. Vital signs

### **7.7.6 Assessments between hospital presentation and hospital discharge**

1. On days of study medication administration (before study administration in those arms where study drug is not an infusion)
  - a. Adverse events of any grade severity present prior to the infusion or medication administration
  - b. Start and stop (or administration time if oral) times of the infusion of the investigational agent/placebo- and restart time if medication stopped for hypotension
  - c. Starting dose of study medication administration
  - d. New adverse events of grade 3-4 severity during and after study medication administration
2. Recording of specifics of study treatment according to assigned arm
3. Daily laboratory assessments as part of routine clinical care (CBC, BMP, LFTs, PT/PTT/INR, D-dimer and CRP).

4. Daily vital signs (including blood pressure), secondary outcomes and safety assessments. In the fostamatinib arm a daily CBC and liver function tests will also be performed.
5. Study-specific blood draws (AngII, Ang(1-7), NT-ProBNP and Troponin) as indicated for each investigational agent in the Ancillary Biomarker Appendix (Appendix C: Minimum Biological Specimen collection).
6. Targeted concomitant medications administered daily in the hospital including remdesivir, Corticosteroids, antiplatelet/anticoagulation, convalescent plasma, monoclonal Ab's, antibacterial agents, antiviral agents against SARS-CoV-2, ACEI's, ARBs, beta blockers.
7. Date and time of first receipt of supplemental oxygen, high-flow nasal cannula, non-invasive ventilation, invasive mechanical ventilation, vasopressors, and extracorporeal membrane oxygenation (if applicable)
8. Date and time of final receipt of supplemental oxygen, high-flow nasal cannula, non-invasive ventilation, invasive mechanical ventilation, vasopressors and extracorporeal membrane oxygenation (if applicable)
9. Pulmonary embolism, systemic arterial thromboembolism, myocardial infarction, or ischemic stroke at hospital discharge or 28 days, whichever occurs first
10. Date and time of first ICU admission
11. Date and time of final ICU discharge
12. Data and time of hospital discharge

### 7.7.7 Assessments following hospital discharge

Patients will be followed through 90 days following randomization. The following data will be collected:

1. Number and reason for missed doses of study drug (only for those discharged prior to completing study drug if applicable)
2. Date of death (if applicable) through day 90
3. ED visits, hospital readmissions, and use of supplemental oxygen, HFNC, NIV, IMV or ECMO after hospital discharge through day 60
4. Safety outcomes (section 5.3.4) after hospital discharge and adverse events as defined in the drug specific appendices and section 13 at day 28 and day 60 (or if discharged earlier as outlined in section 7.1)
5. New or worsening symptoms not previously present at day 28 and day 60 (or if discharged earlier as outlined in section 7.1) including fever, chills, cough, chest pain, dyspnea, headache, sore throat, congestion, runny nose, fatigue, body aches

**Table 1. Schedule of Events**

Event	Baseline & Randomization Day 0	Day 1 – Day 28 	Discharge	Day 60	Day 90
Visit Windows		Day 7 and 14 + 1 Day Day 21 + 2 Days Day 28 + 5 Days		+ 10 Days	+ 14 Days
Confirm eligibility	X				
Obtain informed consent	X				
Screen by reviewing medical history and EMR	X				
Pregnancy test 	X				
Randomization	X				
Concomitant medications	X 	X 			
Record results of SOC laboratory assessments	X 	X			
Study-specific blood draws 					
• CBC with diff and LFTs in fostamatinib arm	X 	X			
Study-specific biological specimen collection 					
• EDTA plasma	X 	X			
• Serum					
Respiratory failure free days, oxygen free days and hospital free days	X 	X	X 		
WHO Ordinal Scale	X	X		X	
Mortality	X	X	X	X	X
Sequential Organ Failure Assessment score	X				
Initiate treatment 	X				
Continue study medication treatment		X			
Adverse event monitoring	X	X 		X	
Record discharge disposition			X		

 Perform events daily through day 28 or discharge, whichever occurs first. Only perform if patient is hospitalized.

 Perform for all women of childbearing potential.

 Perform only if not completed for current admission.

 Perform prior to treatment administration

 Only in the fostamatinib arm if not performed as part of usual care – performed daily while on study drug as an inpatient. A repeat CBC, LFTs and BP check may be necessary depending on values at discharge as indicated in [Appendix D: Arm 3: Fostamatinib](#).

 Coordinate with clinical lab draws when possible- as delineated in [Appendix C: Minimum Biological Specimen collection](#)

 Collect at Day 1, 3, 7, 14, 21, and 28 post-randomization if patient is discharged before 28 days.

 Administration route and timing/frequency is treatment specific

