### 5.3.2 Secondary Outcomes

- Alive and oxygen free at days 14 and 28
- Alive and respiratory failure-free at days 14 and 28
- Alive and free of new invasive mechanical ventilation at 14 and 28 days
- In-hospital, 28-day, 60-day and 90-day mortality
- WHO 8-point ordinal scale at 14, 28 and 60 days
  - 1: Ambulatory – Not hospitalized, no limitation of activities
  - 2: Ambulatory – Not hospitalized with limitation of activities or home oxygen therapy
  - 3: Hospitalized Mild Disease – Hospitalized, no oxygen therapy
  - 4: Hospitalized Mild Disease – Oxygen by mask or nasal prongs
  - 5: Hospitalized Severe Disease – Non-invasive ventilation of high-flow oxygen
  - 6: Hospitalized Severe Disease – Invasive mechanical ventilation
  - 7: Hospitalized Severe Disease – Invasive mechanical ventilation plus

- additional organ support with-vasopressors, RRT, or ECMO
- 8: Dead
- Support-free days to Day 28, including:
  - Hospital-free days
  - Respiratory failure-free days
  - Ventilator-free days

Alive and respiratory failure-free at day 28, the WHO 8-point ordinal scale at day 28, and mortality at day 28 are key secondary outcomes that will be treated as a family for testing purposes, even though the studies will not be adequately powered to detect anything but a very strong treatment effect on these outcomes. A supplementary analysis to assess the evidence that treatment lowers the risk of death in a way that is consistent with its effect on nonfatal outcomes will be performed. A respiratory failure-free day is defined as a day alive without the use of HFNC, NIV, IMV, or ECMO. Participants that are alive but not hospitalized are considered free of respiratory failure.

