7	Hospitalized on invasive mechanical ventilation and other organ support (including vasopressors, RRT or ECMO)	Eligible for enrollment	Classified as day with supplemental oxygen use
8	Death	Patients who die before randomization are not eligible for enrollment	Death at any time prior to the earlier of hospital discharge or day 28 is coded as -1 OFD

The baseline (pre-randomization) clinical status will be used to determine eligibility for enrollment. Clinical status will be scored every day the patient is in the hospital through day 28; these daily scores will be used to calculate OFD.

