3.2 Secondary Outcomes

Listed below are the ACTIV 4 Host Tissue platform secondary outcomes. The “Test Order” field indicates the order in which key secondary outcomes will be tested, using the fixed-sequence method, to control the familywise type-I error probability across the primary and key secondary outcomes.

Description	Type	Test Order	Analysis Method
Alive and oxygen free at day 14	Binary		LogR
Alive and oxygen free at day 28	Binary		LogR
Alive and respiratory failure-free at day 14	Binary		LogR
Alive and respiratory failure-free at day 28	Binary	1	LogR
Alive and free of new IMV at day 14	Binary		LogR
Alive and free of new IMV at day 28	Binary		LogR
Mortality in-hospital	Binary		LogR
Mortality at day 28	Binary	3	LogR
Mortality at day 60	Binary		LogR
Mortality at day 90	Binary		LogR
WHO 8-point ordinal scale at day 14	Ordinal		POLR
WHO 8-point ordinal scale at day 28	Ordinal	2	POLR
WHO 8-point ordinal scale at day 60	Ordinal		POLR
Hospital-free days at day 28	Ordinal		POLR
Respiratory failure-free days at day 28	Ordinal		POLR
Ventilator-free days at day 28	Ordinal		POLR

LogR – Logistic Regression; POLR – Proportional Odds Logistic Regression

The WHO 8-point ordinal scale is defined as most severe clinical status among the following on the day of assessment:

1. Ambulatory – Not hospitalized, no limitation of activities
2. Ambulatory – Not hospitalized with limitation of activities or home oxygen therapy
3. Hospitalized Mild Disease – Hospitalized, no oxygen therapy
4. Hospitalized Mild Disease – Oxygen by mask or nasal prongs
5. Hospitalized Severe Disease – Non-invasive ventilation of high-flow oxygen
6. Hospitalized Severe Disease – IMV
7. Hospitalized Severe Disease – IMV + organ support with-vasopressors, RRT, or ECMO
8. Dead

Alive and respiratory failure-free at day 28, the WHO 8-point ordinal scale at day 28, and Mortality at day 28 are key secondary outcomes that will be treated as a family for testing

purposes, even though the studies will not be adequately powered to detect anything but a very strong treatment effect on these outcomes. A supplementary analysis to assess the evidence that treatment lowers the risk of death in a way that is consistent with its effect on nonfatal outcomes will be performed. A respiratory failure-free day is defined as a day alive without the use of HFNC, NIV, IMV, or ECMO.

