11.3 Model Fitting and Computation

The cumulative logit model is implemented in the R code file “`clm_model.R`”. Readers should examine the `clm_fit` function first, which is the entry point for model fitting, and then examine other functions as they are called by `clm_fit`. The function `clm_fit` takes as arguments the matrix of coded covariates x , and a matrix of coded outcomes y . Each matrix has one row per record (i.e., study participant). The covariate matrix has one column per coded covariate (e.g., age group has three levels and thus requires two columns to distinguish the levels), and the outcome matrix has one column per value that the outcome might take. The cells of the outcome matrix y contain the values y_{ij} as defined above (see “Model Formulation”).

In practice, when one or more levels of an ordinal outcome are not observed in the analysis data set, some of the model intercepts are not estimable (i.e., there is no unique set of model intercepts that maximizes the likelihood/posterior density function). To overcome this, each outcome level is characterized as “estimable” if there is at least one record in the analysis data set where that level is observed and no other level was possible (i.e., ignoring partially observed outcomes), and “not estimable” otherwise. Levels of the outcome that are not estimable are collapsed with the nearest adjacent estimable level to form a new level, e.g., levels 3, 4, and 5 may be collapsed to form level “3|5”. When levels are collapsed, if any collapsed level was possible as part of a partially observed outcome, then the collapsed level is considered possible as well. This functionality is implemented by the function `clmCollapse`, which is called by `clm_fit` prior to any model fitting.

The estimate of θ is found by maximizing the log of the posterior density function (i.e., a maximum *a posteriori* estimate, or MAP for short) defined in expression (5). Note that the normalizing constant in expression (5) is not needed to identify the MAP estimate, nor is it necessary to form a Laplace approximation to the posterior density. The estimate of θ is found using an iterative optimization algorithm, and the associated observed Fisher information is estimated using a finite difference method. These calculations are implemented using the R function `optim`, which uses the quasi-Newton “BFGS” method (Byrd, Lu, Nocedal, and Zhu,

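### As written, the protocol records no activity limitation at days 14 and 28 after discharge, so a discharged patient not on home oxygen can be scored only '1 or 2' on the WHO scale

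*Protocol*

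**What the plan says.** Protocol 5.3.2 lists the outcome as "WHO 8-point ordinal scale at 14, 28 and 60 days". Protocol 8.7 and SAP 3.2 place the day-28 score second among the key secondary outcomes, each tested at one-sided 2.5%. Category 1 is a patient at home without limitation; category 2 is a patient at home with limited activity or on home oxygen.

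Four places describe when the scale is scored:

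- **Protocol Table 1, footnote 1**, on the Day 1 to Day 28 column: "Perform events daily through day 28 or discharge, whichever occurs first. Only perform if patient is hospitalized". The WHO row has plain marks at baseline, in this column and at day 60.
- **Protocol Table 1, footnote 7**: "Collect at Day 1, 3, 7, 14, 21, and 28 post-randomization if patient is discharged before 28 days". It appears on concomitant medications, the free-days row (Discharge column) and adverse events, but not on the WHO row.
- **Protocol Appendix A, section 19.2**: "Clinical status will be scored every day the patient is in the hospital through day 28".
- **Protocol 7.1**: "If the participant is discharged before the full 28-day period, data will be collected according to a set schedule", without itemising the data. The scale is named once: "At day 60 we will collect AEs, the WHO 8-point ordinal scale and assess vital status".

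On analysis, SAP 7.1.1 treats partly known ordinal scores by likelihood. SAP 11.3 adds: "Levels of the outcome that are not estimable are collapsed with the nearest adjacent estimable level to form a new level". SAP 3.2 defines the score by date of contact: "The WHO 8-point ordinal scale is defined as most severe clinical status among the following on the day of assessment".

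**The concern.** A key secondary outcome needs an activity-limitation answer from patients who have gone home, and the schedule does not ask for it at the time point that is tested. These patients are probably a large group at day 28. The step from limited to unlimited activity is also the only part of the scale that can show benefit in a patient already home and off oxygen.

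If that step cannot be scored, all discharged survivors share the top level. Protocol 5.3.2 already counts patients who are alive and out of hospital as free of respiratory failure, so the WHO test would overlap more with the first key secondary outcome. It would also be less sensitive when its turn comes in the sequence. Activity status at day 28 that was never asked for cannot be reliably reconstructed at day 60.

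**Working it through.** **1. What can be scored at day 28 from the items listed.** The sources are Protocol 7.7.7 (post-discharge list), the four telephone questions in 19.2, and the daily in-hospital scoring.

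| Patient's situation at day 28 | Information listed | Score available |
|---|---|---|
| Dead | Date of death through day 90 | 8 |
| In hospital | Daily status; readmission and respiratory support | 3 to 7 |
| Home, using oxygen | Oxygen questions | 2 |
| Home, no oxygen | No activity item | 1 or 2 |

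The symptom item in 7.7.7 covers new or worsening symptoms, which is not the same as limitation of activity. The same table applies at day 14.

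**2. What the analysis would do.** Under SAP 11.3 a level is estimable only if at least one record shows that level and no other. If every patient at home without oxygen is coded '1 or 2', no record is uniquely 1. Level 1 then merges with level 2, which home-oxygen users make estimable. The result is a seven-level scale, with levels 3 to 8 still distinct. The merging is the same in both groups, so type I error does not change.

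**3. Size, for illustration.** The documents give no power figure and no distribution for the day-28 WHO scale, so there is no stated figure to reproduce. For a proportional-odds comparison, information is approximately proportional to 1 − Σp³ (Whitehead), where p are the category proportions.

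Inputs:

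- Deaths: 17.6%, 18.6% and 23.5%, from Protocol 8.6.5 and SAP 6.6.
- Discharged at day 28: 50%, 60% and 70% (assumed).
- Category-1 share of the discharged: 10%, 25%, 50%, 75% and 90% (assumed).
- Remainder spread over categories 3 to 7 in proportions 15, 35, 20, 20 and 10% (assumed).

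Worked case: 18.6% dead, 60% discharged, split evenly.

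- Remainder: 1 − 0.186 − 0.600 = 0.214. Its five cubes sum to 0.0006, and 0.186³ = 0.0064.
- Full scale: 1 − 2 × 0.300³ − 0.0064 − 0.0006 = 0.939.
- Levels 1 and 2 merged: 1 − 0.600³ − 0.0064 − 0.0006 = 0.777.
- Ratio: 0.777 / 0.939 = 0.83, a loss of about 17%.

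Selected results, including the extremes of all 45 combinations:

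| Dead | Discharged | Share in category 1 | Full | Merged | Kept |
|---|---|---|---|---|---|
| 17.6% | 50% | 90% | 0.901 | 0.867 | 96% (smallest loss, about 4%) |
| 18.6% | 60% | 10% | 0.835 | 0.777 | 93% |
| 18.6% | 60% | 50% | 0.939 | 0.777 | 83% |
| 23.5% | 70% | 50% | 0.901 | 0.644 | 71% (largest loss, about 29%) |

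A second mix uses 23.5% dead, 43% home without oxygen, 15% home on oxygen and 18.5% in hospital. Averaging the two groups at an odds ratio of 1.65, it loses 17% to 21% when 30% to 70% of the 43% are in category 1, and about 8% when 10% are. The loss is always in one direction, but its size follows from a share that nobody has documented.

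**The case against.** The strongest reply is that the documents do not show that the score goes uncollected.

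- Footnote placement is a weak guide. The Mortality row also has a plain mark in the Day 1 to Day 28 column without footnote 7, yet 28-day mortality is plainly intended.
- The list in 7.7.7 has no activity item for day 60 either, although the scale is explicitly scheduled then. That list is therefore not exhaustive for WHO scoring.
- The four questions in 19.2 are introduced as the home-oxygen assessment, not as the whole call. SAP section 10 refers to a telephone script and an outpatient form, which are not among the documents.
- Section 7.1 and the Table 1 windows do plan day-14 and day-28 contacts, and their unitemised data could include the scale.
- Both documents already concede that power is low for these outcomes for anything but a very strong effect, and the test is reached only after two earlier successes.

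Most of this stands. A reader might infer that the day-28 score is definitely not collected; the documents support only that they do not provide for it. The Mortality comparison has a limit, however: date of death is separately listed in 7.7.7, whereas day-28 activity limitation has no such backup. An outcome that is formally tested should not depend on an unseen form when Table 1 and Appendix A point the other way.

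A reader might also infer from SAP 3.2 and the +5-day window that a death on day 30, before the call, becomes category 8 at day 28. That is strained: the outcome is named for day 28, and the date of death is recorded.

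**Conclusion.** The gap holds in a limited form. As written, categories 1 and 2 cannot be told apart at days 14 and 28 in discharged patients not on home oxygen. Every other patient can be scored. The test of the second key secondary outcome can still be run, with type I error intact and levels 3 to 8 distinct, so the outcome is coarsened rather than lost.

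The merging under SAP 11.3 is conditional: it follows only if no patient is recorded uniquely in category 1. The loss of about 4% to 29% of information is illustrative. It rests on assumed discharge and category-1 shares and on an assumed spread over categories 3 to 7; only the death proportions come from the documents. A single power loss should not be quoted. The point justifies a small amendment because it concerns data that must be collected at the time.

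**What to change.** 1. In Protocol Table 1, attach footnote 7 to the WHO row, at least for days 14 and 28.
2. Add one question to the existing day-14 and day-28 contacts: was the patient limited in usual activities on that study day? If the outpatient form already has this item, cite it in Table 1 and SAP 3.2 instead.
3. As a minor wording alignment, have SAP 3.2 score status on the named study day (14, 28 or 60), whatever the date of contact.

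The cost is one footnote, one question in calls already planned, and one SAP phrase. The downside is a few days of recall when the contact falls late in its window.
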